6.4 Dose Escalation

6.4.1 Dose Escalation Design

The dose escalation of loncastuximab tesirine in Phase 1 will follow a standard 3+3 design using the dose levels defined in [Section 6.5](#). The dose one dose level below the dose at which ≥33% of patients experience a DLT will be considered the MTD. Cohorts of 3 patients will be treated, starting at the initial dose level. If 0 of 3 patients in the first cohort at any dose level experience a DLT, then the following cohort will be treated at the next higher dose level. If 2 of 3 patients experience a DLT, then the preceding dose level will be determined as the MTD. If 1 of 3 patients experiences a DLT, then 3 additional patients will be treated at that dose level. If 0 of the 3 additional patients experience a DLT, then the following cohort will be treated at the next higher

dose level. If 1 or more of the 3 additional patients experience a DLT, then the preceding dose level will be determined as the MTD.

There will be a minimum of 5 days between dosing the first and second patient at each dose level during dose escalation.

Patients who discontinue from the study prior to completion of the DLT Period without a DLT will be replaced.

6.4.2 Dose-Limiting Toxicity Period

The first 21 days of ibrutinib administration will be considered the DLT Period for patients in Phase 1 dose escalation who are following the 3+3 study design.

6.4.3 Dose-Limiting Toxicity Definition

A DLT is defined as any of the following events which occur during the DLT Period, except those that are clearly due to underlying disease or extraneous causes:

A hematologic DLT is defined as:

- Grade 4 anemia
- Grade 3 anemia requiring transfusion
- Grade 4 neutropenia lasting > 7 days
- Febrile neutropenia
- Grade 4 thrombocytopenia
- Grade 3 thrombocytopenia which results in clinically significant bleeding or requires a transfusion

A non-hematologic DLT is defined as:

- Hy's law case: AST and/or ALT > 3 × ULN and bilirubin > 2 × ULN, and without initial findings of cholestasis (serum alkaline phosphatase [ALP] activity < 2 × ULN) and no other reason that could explain the combination of increased transaminases and serum total bilirubin
- Any other non-hematologic toxicities \geq Grade 3, with the exception of the following conditions:
 - Grade 3 fatigue for \leq 7 days.
 - Grade 3 nausea, vomiting, or diarrhea in the absence of premedication that responds to therapy and improves by at least 1 grade within 3 days or to \leq Grade 1 within 7 days.
 - Grade 3 elevations of ALP and GGT elevations, unless considered clinically relevant by the Investigator.
 - Grade 3 elevation of serum lipase or serum amylase for \leq 7 days if without clinical signs or symptoms of pancreatitis.

- Grade 3 electrolyte abnormalities which normalize within 48 hours (with or without medical intervention) and which do not manifest themselves clinically; in such instance, a follow-up sample MUST be taken within 48 hours to check whether such normalization has occurred.

Patients who experience a DLT that resolves or stabilizes with appropriate medical management may continue treatment at the discretion of the Investigator in consultation with the Sponsor.

6.4.4 Dose Escalation Steering Committee

A DESC will oversee dose escalation and general safety of the study.

Membership of the DESC will include:

- Medical and/or pharmacovigilance representative(s) from the Sponsor and/or designee
- Investigator(s) from each participating site

The DESC will be responsible for:

- Determining dose levels to be administered and the MTD based on assessment of safety findings and DLTs.
- Monitor the safety of the study and review its progress at monthly intervals or more frequently as required.

Decisions made at DESC meetings will be documented in written minutes that will be distributed to DESC members.

6.5 Dose Delays and Modifications

6.5.1 Loncastuximab Tesirine

Table 6 Loncastuximab Tesirine Guidelines for Dose Modifications

Study Drug	Loncastuximab Tesirine
Grade ≥ 2 edema, effusion All other non-hematologic AEs Grade ≥ 3	
 Loncastuximab tesirine must be held until the toxicity resolves to Grade ≤ 1, (Grade 1 or baseline for peripheral neuropathy) If loncastuximab tesirine dosing is delayed by more than 3 weeks and the toxicity is considered at least possibly related to loncastuximab tesirine, then subsequent doses of loncastuximab tesirine will be reduced by 50% Investigator may reduce the dose of loncastuximab tesirine by 50% if the toxicity is possibly related to loncastuximab tesirine, but does not result in dosing delay of more than 3 weeks if they feel it is in the best interest of the patient
Grade ≥ 3 neutropenia or thrombocytopenia	
 Loncastuximab tesirine must be held until toxicity resolves to Grade ≤ 2 If loncastuximab tesirine dosing is delayed by more than 3 weeks and the toxicity is considered at least possibly related to loncastuximab tesirine, then subsequent doses of loncastuximab tesirine will be reduced by 50% Investigator may reduce the dose of loncastuximab tesirine by 50% if the toxicity is possibly related to loncastuximab tesirine, but does not result in dosing delay of more than 3 weeks if they feel it is in the best interest of the patient
Skin related toxicities including photosensitivity rash Grade ≤ 2	
No dose adjustment is required.
 
Topical treatment to affected areas is indicated:
 
 maculopapular rash, photosensitivity rash: high potency topical steroid cream (e.g., clobetasol propionate 0.05%, halobetasol propionate 0.05%) pruritus: high potency topical steroid cream (e.g., clobetasol propionate 0.05%, halobetasol propionate 0.05%) and consider oral antipruritic xerosis or hyperpigmentation: consider ammonium lactate 12% or urea 20% BID blistering rash: silvadene 1% cream BID and consider laboratory testing for blistering disorder (VZV/HSV and bacterial infection; bullous pemphigoid; pemphigus). 
Periodic reassessment as indicated
 
For Grade 2, the Sponsor recommends dermatological consultation

Table continued on next page.

Study Drug	Loncastuximab Tesirine
Skin related toxicities including photosensitivity rash Grade \geq 3	
Hold loncastuximab tesirine until improvement to \leq Grade 1 and consider dermatological consultation
 
Topical treatment to affected areas is indicated:
 
 maculopapular rash or photosensitivity rash: high potency topical steroid cream (e.g., clobetasol propionate 0.05%, halobetasol propionate 0.05%) and consider systemic prednisone 0.5 mg/kg for 10 days pruritus: high potency topical steroid cream (e.g., clobetasol propionate 0.05%, halobetasol propionate 0.05%) and consider oral antipruritic. xerosis: consider ammonium lactate 12% or urea 20% BID; and triamcinolone 0.1% cream BID. blistering rash: silvadene 1% cream BID and consider laboratory testing for blistering disorder (VZVHSV and bacterial infection; bullous pemphigoid; pemphigus) and systemic prednisone 0.5 mg/kg for 10 days 
Periodic reassessment as indicated.
 
If loncastuximab tesirine dosing is delayed by more than 3 weeks and the toxicity is considered at least possibly related to loncastuximab tesirine, then subsequent doses of loncastuximab tesirine will be reduced by 50%.
 
The Investigator may also reduce the dose of loncastuximab tesirine by 50% for any Grade \geq3 toxicity that is possibly related to loncastuximab tesirine but does not result in dosing delay of more than 3 weeks if they feel it is in the best interest of the patients.

Grade 4 infusion related reactions	Permanently discontinue loncastuximab tesirine
Hy's law (AST and/or ALT $> 3 \times$ ULN and bilirubin $> 2 \times$ ULN)	
Permanently discontinue loncastuximab tesirine.
 
Hy's law defined as: AST and/or ALT $> 3 \times$ ULN and bilirubin $> 2 \times$ ULN, and without initial findings of cholestasis (ALP activity $< 2 \times$ ULN) and no other reason that could explain the combination of increased transaminases and serum total bilirubin, such as viral hepatitis A, B, or C, preexisting or acute liver disease, or another drug capable of causing the observed injury

For ibrutinib dose modification guidance, please see [Section 6.5.2](#).

If loncastuximab tesirine dosing is delayed or discontinued and the toxicity is at least possibly related to locastuximab tesirine, ibrutinib dosing can continue at the discretion of the Investigator and in consultation with the Sponsor.

6.5.2 Ibrutinib

For any Grade 2 AE, a dose reduction can occur at the discretion of the Investigator and in consultation with the Sponsor.

If a patient experiences any Grade ≥ 3 toxicity, ibrutinib must be held until the toxicity resolves to Grade 1 or baseline. Once the symptoms of the toxicity have resolved to Grade 1 or baseline, ibrutinib therapy may be reinitiated at the original dose.

If toxicity as described above recurs and is considered at least possibly related to ibrutinib, after a dose hold, subsequent doses of ibrutinib will be reduced by 140 mg to 420 mg daily, or to 280 mg daily where applicable.

If toxicity as described above recurs at the reduced dose and is considered at least possibly related to ibrutinib, after a dose hold, subsequent doses of ibrutinib will be reduced by an additional 140 mg to 280 mg daily, or to 140 mg daily where applicable.

If toxicity as described above recurs after a second dose reduction and is considered at least possibly related to ibrutinib, ibrutinib must be discontinued permanently.

For Grade 3 or 4 atrial fibrillation or persistent atrial fibrillation of any grade, consider the risks and benefits of ibrutinib treatment. If clinically indicated, the use of anticoagulants or antiplatelet agents may be considered for the thromboprophylaxis of atrial fibrillation.

Ibrutinib is metabolized primarily by CYP3A4. Avoid concomitant use of systemic strong or moderate CYP3A inhibitors and consider alternative agents with less CYP3A inhibition.

If a strong CYP3A inhibitor must be used, reduce ibrutinib dose to 140 mg or withhold treatment for the duration of inhibitor use. Subjects should be monitored for signs of ibrutinib toxicity. If a moderate CYP3A inhibitor must be used, reduce ibrutinib to 140 mg for the duration of the inhibitor use. Avoid grapefruit and Seville oranges during ibrutinib treatment, as these contain moderate inhibitors of CYP3A. No dose adjustment is required in combination with mild inhibitors.

If the dose of ibrutinib is reduced as per protocol the dose of ibrutinib may be re-escalated, at the investigator's discretion upon discussion with the sponsor, after at least 2 months of a dose reduction in the absence of a recurrence of the toxicity that led to the reduction.

If a dose of ibrutinib is not taken at the scheduled time, it can be taken as soon as possible on the same day with a return to the normal schedule the following day. Extra doses of ibrutinib should not be taken to make up for the missed dose.

If ibrutinib dosing is delayed or discontinued and the toxicity is at least possibly related to ibrutinib, loncastuximab tesirine dosing can continue at the discretion of the Investigator and in consultation with the Sponsor.

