3 STUDY OBJECTIVES AND ENDPOINTS

Table 3 Study Objectives and Endpoints

Primary	
Objectives	Endpoints

Phase 1:
 
• To characterize the safety and tolerability of loncastuximab tesirine in combination with ibrutinib, and to identify the MTD/recommended dose and schedule for future studies 
Phase 2:
 
• To evaluate the efficacy of loncastuximab tesirine given at every cycle in combination with ibrutinib in patients with relapsed or refractory DLBCL	
Phase 1:
 
• Frequency and severity of adverse events (AEs) and serious adverse events (SAEs)• Incidence of dose-limiting toxicities (DLTs) (dose escalation only)• Frequency of dose interruptions and dose reductions• Changes from baseline of safety laboratory values, vital signs, Eastern Cooperative Oncology Group (ECOG) performance status, and 12-lead electrocardiograms (ECGs) 
Phase 2:
 
• CRR according to the 2014 Lugano classification (Cheson et al., 2014) as determined by independent review committee (IRC) in all DLBCL patients given loncastuximab tesirine at every cycle in combination with ibrutinib; CRR defined as the proportion of patients with a best overall response (BOR) of complete response (CR)

Table continued on next page.

Secondary	
Objectives	Endpoints

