9.6 Exposure to Treatments

Exposure to study drug and prior and concomitant medications will be summarized for the Safety population. Dose interruptions, reductions, and relative dose intensity will also be summarized.

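### For an acute Grade 3 or higher event attributed to one study drug, the protocol both requires the other drug to be held and permits it to continue, and does not say which rule prevails

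*Protocol*

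**What the plan says.** Four sentences in Protocol Section 6.5 govern what happens to each drug.

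- **Ibrutinib, hold (6.5.2).** For any Grade 3 or higher "toxicity, ibrutinib must be held until the toxicity resolves to Grade 1 or baseline". Attribution to ibrutinib enters only in the later paragraphs, on dose reduction and discontinuation after recurrence.
- **Ibrutinib, continuation (6.5.1, closing paragraph).** If loncastuximab tesirine is delayed or discontinued for a toxicity at least possibly related to it, "ibrutinib dosing can continue at the discretion of the Investigator and in consultation with the Sponsor". No grade limit is given.
- **Loncastuximab tesirine, hold (6.5.1, Table 6).** For edema or effusion of Grade 2 or higher and all other non-hematologic AEs of Grade 3 or higher: "Loncastuximab tesirine must be held until the toxicity resolves to Grade ≤ 1". For Grade 3 or higher neutropenia or thrombocytopenia: "Loncastuximab tesirine must be held until toxicity resolves to Grade ≤ 2". Attribution matters in these rows only for the 50% dose reduction, not for the hold.
- **Loncastuximab tesirine, continuation (6.5.2, last paragraph).** If ibrutinib is delayed or discontinued for a toxicity at least possibly related to it, "loncastuximab tesirine dosing can continue at the discretion of the Investigator and in consultation with the Sponsor". Again there is no grade limit.

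Protocol Section 3 lists "Frequency of dose interruptions and dose reductions" as a Phase 1 primary endpoint. Protocol Section 9.6 adds: "Dose interruptions, reductions, and relative dose intensity will also be summarized".

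**The concern.** Each hold is worded as mandatory and ignores attribution. Each continuation clause is a permission that depends on attribution to the other drug and has no upper grade. A Grade 3 event attributed to one drug can meet both conditions, and the text gives opposite answers for the other drug. Neither hold sentence contains an exception, and neither continuation clause says that it yields to the hold.

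Two things are at stake. The first is patient safety: a site can withhold or give the second drug for the same event and cite the protocol for either. The second is interpretation: a recorded interruption may reflect the sentence that was followed rather than the tolerability of the regimen, and a dose given through such an event cannot be classed as compliant or as a deviation until one rule prevails.

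**Working it through.** The plan has no figure to reproduce here, so the check sets the rules side by side.

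| Situation | Ibrutinib | Loncastuximab tesirine | Conflict? |
|---|---|---|---|
| Acute Grade ≥3 non-hematologic AE, neutropenia or thrombocytopenia, attributed to loncastuximab tesirine | 6.5.2: hold. 6.5.1 closing paragraph: may continue | Table 6: hold | Yes, over ibrutinib |
| Same events, attributed to ibrutinib | 6.5.2: hold | Table 6: hold. 6.5.2 last paragraph: may continue | Yes, over loncastuximab tesirine |
| Grade 2 edema or effusion, attributed to loncastuximab tesirine | 6.5.2: no hold required. 6.5.1: may continue | Table 6: hold | No |
| Grade ≥3 anemia, attributed to ibrutinib | 6.5.2: hold | No Table 6 hold. 6.5.2: may continue | No |
| Neutropenia or thrombocytopenia recovered to Grade 2 | 6.5.2: still held unless Grade 2 is baseline | Table 6 hold ended. 6.5.2: may continue | No |
| One drug permanently discontinued, the other's own hold resolved | May continue | May continue | No |

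The conflict is therefore confined to the first two rows, but it runs in both directions.

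**Where it reaches the analysis**

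- *Interruptions.* SAP Section 5.8.1 summarises delay, reduction and interruption for loncastuximab tesirine only. For ibrutinib they enter through the summary in SAP Section 5.10.1.1 of TEAEs leading to a delayed, reduced or interrupted dose of either drug. In Phase 1, loncastuximab tesirine is due only at Cycles 1 and 2 and possibly 5 and 6 (Protocol Section 4.3), so the effect falls mainly on daily ibrutinib.
- *Ibrutinib relative dose intensity.* In SAP Section 5.8.1 the denominator for Phase 1 and the intermittent cohort is treatment duration × 560 mg/day, and duration runs from first to last dose. If h days are held within a duration of D days and the other doses are taken in full, relative dose intensity is 100 × (D − h)/D, a loss of 100 × h/D percentage points. If ibrutinib continues through the event, there is no loss.
- *Deviations.* SAP Section 5.3 treats an incorrect dose as an important deviation, and SAP Section 5.1.6 removes patients with major deviations from the Per Protocol Set. Neither section says how a dose given or withheld under the conflicting text is classed.

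**Scale, by assumption only.** Let N be the number of Phase 1 patients, q the share with a Grade ≥3 event attributed to loncastuximab tesirine that delays it, and f the share of those who continue ibrutinib. If every site follows the hold, N × q patients have an ibrutinib interruption for this reason. If the permission is used, N × q × (1 − f) do. The difference is N × q × f, at most N × q, and less if some of these patients also interrupt ibrutinib for another reason.

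The documents give no q or f for the combination. With N = 47 (SAP Section 4.1) and f = 1:

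- q = 10%: 47 × 0.10 = 4.7, about 5 patients
- q = 20%: 47 × 0.20 = 9.4, about 9 patients
- q = 40%: 47 × 0.40 = 18.8, about 19 patients

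With f = 0.5 each is halved. These are ceilings under assumed inputs, not estimates.

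**The case against.** **Sponsor consultation.** Both continuation clauses require consultation with the Sponsor as well as Investigator discretion. One Sponsor advises all sites, which could make practice uniform. This stands: the text supports saying that sites can act differently, not that they will. It does not remove the contradiction, because a consultation cannot turn a mandatory hold into an option unless the hold sentence allows for it.

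**A harmonising reading.** The clauses may mean only that delaying one drug does not by itself stop the other, with each drug's own hold still governing. They would then keep real uses, namely the last four rows of the table. Grade 3 or higher anemia is not rare: it occurred in 10.3% of patients on monotherapy (Protocol Section 1.2.2.2). This is reasonable, and it means that the clauses should not be called empty or contradictory in nearly every use. But the protocol does not state this reading, and a site could equally read the clauses as exceptions.

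**The endpoint.** A reader might infer that the Phase 1 primary endpoint is distorted. The documents do not support that. The endpoint is descriptive, with no test or threshold, and the eCRF records relationship to study drug(s) and action taken (Protocol Section 8.2.2), so candidate cases can be found and reviewed.

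**A patient count.** A reader might also apply the 72.4% monotherapy rate of Grade 3 or higher TEAEs (105 of 145, Protocol Section 1.2.2.2) to all 136 patients in the SAP. That rate is for any cause and comes from monotherapy at a different dose, and 89 of the 136 are Phase 2 patients, to whom the Phase 1 endpoint does not apply. It does not measure how often the conflict arises.

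**Conclusion.** The contradiction is in the text, runs in both directions and has no stated precedence. It is limited to acute Grade 3 or higher events that are attributed to one drug and fall within a mandatory hold for the other. The Phase 1 interruption endpoint, ibrutinib relative dose intensity and the classification of dosing deviations can depend on which sentence was followed. By how much cannot be estimated from the documents, and the counts above rest wholly on assumed values of q and f.

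Severity is should-fix. No hypothesis test depends on this point. The SAP reports early termination (Section 1) and says that the every-cycle cohort will not be enrolled (Section 4). New wording protects patients only while some remain on treatment, but the classification question for reporting remains either way. Which clinical rule is right is not judged here.

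**What to change.** 1. **Protocol.** Reconcile Section 6.5.1, Table 6 and Section 6.5.2 so that one rule is stated to prevail for a Grade 3 or higher toxicity attributed to one drug. The opposing sentence becomes either an explicit exception to the hold or is limited to events that the hold does not cover. The sponsor and the DESC decide which.
2. **SAP, before database lock.** State how doses given or withheld under the conflicting text are classified for protocol deviations and in the interruption summaries. Use the recorded relationship and action-taken fields to identify the cases. The documents describe no field that marks an interruption as mandated or discretionary, so a split on that basis should not be promised unless such a record exists.

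The cost is a wording change in two protocol subsections, handled under the amendment process in Protocol Section 11.8, a note to sites if any patients remain on treatment, and a short SAP paragraph. No new data are needed.

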6.6 Overdose Management

An overdose is any dose of study drug(s) given to a patient that exceeds by 15% of the dose described in the protocol. Any overdose, with or without associated AEs, must be promptly reported to the Sponsor. There are no data available to determine what the effects of overdose of loncastuximab tesirine are and whether they can be reversed. There is no specific experience in the management of ibrutinib overdose in patients. Symptomatic treatment and standard supportive care measures for the management of any observed toxicity should be applied.

6.7 Premedication and Supportive Care

6.7.1 Premedication for Loncastuximab Tesirine

Unless contraindicated, administer dexamethasone 4 mg po twice daily:

- the day before each loncastuximab tesirine administration (if possible),
- the day of loncastuximab tesirine administration (first dose at least 2 hours prior to administration when not given the day before; otherwise, any time prior to administration), and
- the day after loncastuximab tesirine administration.

Dexamethasone may be given IV in patients unable to take po.

Patients who experience an infusion-related hypersensitivity reaction will receive the alternative premedication regimen specified in [Section 6.7.3](#).

6.7.2 Treatment of Edema and Pleural Effusion

Peripheral edema and serosal effusions (pleural and pericardial effusions, ascites) have been seen in patients receiving loncastuximab tesirine. Patients should be advised to monitor their weight on a daily basis (preferably each morning around the same time) and notify the study site of weight gain greater than 1 kg from baseline.

Patients with weight gain greater than 1 kg from baseline, new or worsening edema, and/or new or worsening pleural effusion, pericardial effusion, or ascites, should be treated with spironolactone at standard doses. The dose of spironolactone may be titrated as clinically indicated. Additional diuretic support may be added if there is further increase in weight, edema, or effusion.

